### 6.2.5 Rules for Intracranial/Brain Edema

Development of edema in the brain or central nervous system necrosis is common following fractionated brain radiation therapy and may be asymptomatic (solely a radiographic finding) or associated with mild, moderate or severe symptoms. Therefore, brain edema will be considered an **expected** event related to study therapy (RT) and will **not** be considered a DLT and will not require permanent study drug discontinuation unless symptoms from brain/intracranial edema meets criteria for discontinuation below.

**Note**, the CTCAE v4.03 term "**Edema cerebral**" only has grade 4 classification in the CTCAE v4.03. Therefore, the "Edema cerebral" CTCAE v4.03 term should be used only if the event meets **grade 4 criteria** per CTCAE v4.03 criteria (i.e., life-threatening consequences; urgent intervention indicated). **Grade 4 Edema cerebral** is defined by any of the following criteria:

- Any neurosurgical procedure is required to manage brain edema
- Requires mannitol for management of symptomatic brain edema
- Requires  $> 8$  mg per day of dexamethasone or bioequivalent for more than 7 consecutive days to manage symptoms of brain edema

CONFIDENTIAL

This material is the property of the NYU School of Medicine. Do not disclose or use except as authorized in writing by the study sponsor

- Brain edema is deemed life-threatening per judgment of the treating investigator

For study purposes, the AEs deemed attributable to brain or intracranial edema that do not meet "Edema cerebral (Grade 4)" criteria per CTCAE v4.03 should be described by the symptom (e.g. headache, nausea, focal neurological deficit) and graded for severity accordingly. In addition, the term "Nervous System Disorders - Other" may be used with a description to specify the AE.

If appropriate, the investigator should use the term "**Central nervous system necrosis**" per CTCAE 4.03 criteria if the investigator deems the radiographic findings are consistent with central nervous system radiation necrosis without symptomatic Grade 4 severity.

#### **6.2.5.1 Criteria for Nivolumab and Ipilimumab Dose Delay and Discontinuation for symptoms attributable to brain or intracranial edema or central nervous system necrosis:**

- **Grade ≤3 AEs** that are attributable **brain/intracranial edema or central nervous system necrosis** will not be classified as DLT (if in the Safety Lead-In cohort) and will not require permanent study drug discontinuation if:
  - The grade 3 AE downgrades to Grade ≤1 within 7 days after onset of the event with maximal supportive care, including bevacizumab (see bevacizumab guidelines below) and/or systemic corticosteroid administration (no more than 7 consecutive days of dexamethasone dosed at >8 mg per day or bioequivalent).
  - The grade 2 AE improves to grade ≤1 or baseline within 7 days after onset of the event with maximal supportive care, including bevacizumab and/or systemic corticosteroid administration (no more than 7 consecutive days of dexamethasone dosed at >8 mg per day or bioequivalent).
- **Grade 4** symptoms attributable to brain or intracranial edema or central nervous system necrosis will be considered a DLT and require immediate discontinuation of nivolumab and ipilimumab.
- **Grade 4 "Edema cerebral"** will be considered a DLT require immediate discontinuation of nivolumab and ipilimumab.

Subjects who experience Edema cerebral Grade 4 will be classified as having a DLT (if in the Safety Lead-In cohort) and will discontinue nivolumab and ipilimumab immediately and will enter the post-study follow-up phase of the study. The overall PI may request additional information on events classified as Grade 4 cerebral edema.

**Note on Pseudoprogression:** Tumor infiltration with immune cells may be associated with increasing enhancement and edema on brain MRI or CT (i.e. **pseudoprogression**) and may mimic therapy-related central nervous system radiation necrosis or disease progression. Due to the well-described difficulty in differentiating between immune-mediated pseudoprogression and true tumor progression using standard imaging techniques, particularly in brain tumors, special attention must be made to events that are suspected to be attributed to possible brain edema and central nervous system necrosis.

**For guidelines on managing radiographic findings of possible treatment-related brain edema, progression or pseudoprogression**, refer to Efficacy Procedures and Appendix 3, **iRANO criteria**. A symptom or AE is initially suspected to be due to pseudoprogression or central nervous system necrosis may be later considered to be due to disease progression after review of additional imaging, biopsies and consultations with the treating investigators by the Sponsor. These events may be reviewed during the Safety Lead-In and toxicity monitoring during the phase II trial.

#### **6.2.6 Bevacizumab for Symptoms Related to Intracranial Edema**

CONFIDENTIAL

This material is the property of the NYU School of Medicine. Do not disclose or use except as authorized in writing by the study sponsor

For subjects who are suspected to have study treatment-related symptomatic intracranial or brain edema at any time during the study, nivolumab and ipilimumab dosing should be immediately interrupted. **VEGF inhibition is preferred over corticosteroids** for management of suspected intracranial or brain edema, radiation necrosis, or intracranial hypertension, due to the risk that corticosteroids may suppress immune response against the tumor. Bevacizumab was granted accelerated approved by the US FDA for use as monotherapy in progressive GBM based on two historically-controlled, single-arm or non-comparative phase II trials,, however the addition of bevacizumab to standard of care in newly diagnosed GBM or to lomustine in recurrent GBM failed to show a benefit in overall survival in multi-institutional, randomized phase III trials. Therefore, the addition of bevacizumab should not alter the survival outcomes of the study regimen.

The VEGF inhibition strategy will be **bevacizumab (at a maximal dose of 10 mg/kg IV) every 2 weeks, for a minimum of 2 doses**. Nivolumab and ipilimumab may resume when symptoms related to cerebral inflammation have resolved to grade  $\leq 1$  or baseline. If treatment with nivolumab and ipilimumab is resumed, bevacizumab can be continued in conjunction with these agents as deemed appropriate but the investigator.

If VEGF inhibition does not resolve the symptoms to grade  $\leq 1$  or baseline, the investigator may institute systemic corticosteroids, in addition to or as a replacement for bevacizumab, at the lowest dose that is appropriate for symptom management.

If the symptoms have not improved to grade  $\leq 1$  or baseline by 7 days after symptom onset, the subject will come off study. If a subject requires a neurosurgical procedure or mannitol to manage grade  $\geq 3$  symptom attributable to intracranial or brain edema, or if the symptoms have not improved to grade  $\leq 1$  or pre-treatment baseline by 7 days after symptom onset, the AE will be considered a DLT (if in the Safety Lead-in cohort) and the subject will discontinue study therapy.

**Table 2: Guidelines for Nivolumab and Ipilimumab Hold and/or Discontinuations for Symptoms Related to Intracranial/Brain Edema or Central Nervous System Necrosis**

Grade	Hold Nivolumab and Ipilimumab?	Restarting Criteria	Discontinuation Criteria
1	No	N/A	N/A
2	Consider withholding for persistent symptoms Consider bevacizumab if symptoms persist 	Toxicity resolves to Grade 0–1 or baseline within 7 days	Toxicity does not resolve to Grade $\leq 1$ or baseline within 7 days of symptom onset or requires $>8$ mg/day of dexamethasone or bioequivalent for $>7$ consecutive days to treat symptoms.
3	Yes Initiate bevacizumab in addition to appropriate symptomatic treatment 	Toxicity resolves to Grade $\leq 1$ or baseline within 7 days	

• Toxicity does not resolve to Grade <math>\leq 1</math> or baseline within 7 days

• Requires <math>>8</math> mg/day of dexamethasone or bioequivalent for <math>>7</math> consecutive days to treat symptoms

• Requires a neurosurgical procedure or mannitol to manage symptoms

4 	Discontinue	N/A	Patient must be discontinued

Note: Per CTCAE v4.03, the AE "Edema cerebral" only has Grade 4 severity. The AE "Edema cerebral" should be used only if the symptom severity meets the CTCAE v4.03 criteria (i.e., "Life-threatening consequences; urgent intervention indicated"). See **Rules for Brain Edema, Section 6.2.5**

CONFIDENTIAL

This material is the property of the NYU School of Medicine. Do not disclose or use except as authorized in writing by the study sponsor

 For subjects who develop symptoms of **Grade ≤3** attributable to **brain edema or central nervous system necrosis**, maximal supportive care and symptomatic treatment, including bevacizumab and/or systemic corticosteroids, should be administered as clinically appropriate. **VEGF inhibition is preferred over corticosteroids** for management of suspected intracranial or brain edema, radiation necrosis, or intracranial hypertension. The VEGF inhibition strategy will be **bevacizumab (at a maximal dose of 10 mg/kg IV) every 2 weeks, for a minimum of 2 doses**. Systemic corticosteroids should be given for the lowest duration and dose required to treat symptoms in order to avoid significant immunosuppression. If corticosteroids are required, a taper should be considered once symptoms improve to Grade 1 or less and tapered over at least 4 weeks if doses >4 mg/day of dexamethasone or bioequivalent are administered for >7 days.

 Subjects who experience **Edema cerebral, Grade 4** per CTCAE v4.03 criteria, must discontinue nivolumab and ipilimumab. For study criteria that qualify for Grade 4 Edema cerebral see **Rules for Brain Edema** (Section 6.2.5).

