#### 6.1.1.1 **Definition of Dose-Limiting Toxicity (DLT) for the Safety Lead-In**

The DLT period for the Safety Lead-In is considered the first 40 days of study therapy, and will include labs and other evaluations taken at C1D40 (end of the first 40 days). The frequency, time to onset, and severity of toxicities, as well as the success of standard medical management and dosing interruptions/ delays, will be analyzed to determine if a given toxicity should be considered a DLT for dose decision purposes. The final decision of whether or not the AE meets the DLT definition will be based on a careful review of all relevant data by the Sponsor and the NYU DSMC. The treating investigator may also be consulted.

A DLT is defined as any non-hematologic grade  $\geq 3$  adverse event (AE) that is at least possibly, probably or definitely related to nivolumab or ipilimumab or RT during the DLT period with the exceptions noted below.

The following will be classified as DLT:

- Any Grade 2 drug-related uveitis or eye pain or blurred vision that does not respond to topical therapy and does not improve to Grade 1 severity within 7 days OR requires systemic treatment.
- Any Grade  $\geq 2$  drug-related pneumonitis or interstitial lung disease that does not resolve to Grade 1 within 7 days and systemic steroids (also see Pulmonary Adverse Event Management Algorithm in Appendix 4).
- Any Grade 3 drug-related bronchospasm, hypersensitivity reaction, or infusion reaction, regardless of duration.
- Any Grade 3 non-hematologic, drug-related adverse event, with the following criteria:
  - Grade 3 drug-related uveitis, pneumonitis, diarrhea, or colitis of any duration will be classified as DLT.
  - Grade  $\leq 3$  symptoms attributable to brain/intracranial edema that downgrades to Grade  $\leq 2$  within 7 days, or to Grade  $\leq 1$  or baseline within 14 days after onset will not be classified as DLT (for **rules for managing brain/intracranial edema**, see Section 6.2.5 below).
  - Any  $\geq$  grade 2 neurological AE lasting  $> 7$  days will be considered a DLT.
- Grade  $\geq 3$  thrombocytopenia ( $< 50,000 \text{ mm}^3$ ), which will be classified as DLT
- Grade  $\geq 3$  neutropenia ( $\text{ANC} < 1000 \text{ mm}^3$ ), which will be classified as DLT
- Any drug-related liver function test (LFT) abnormality that meets the following criteria will be classified as DLT (also see Hepatic Adverse Event Management Algorithm):

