#### 6.2.4.1 Nivolumab Dose Discontinuation

Treatment with nivolumab should be permanently discontinued for any of the following:

- Any Grade 2 drug-related uveitis or eye pain or blurred vision that does not respond to topical therapy and does not improve to Grade 1 severity within the treatment re-initiation period OR requires systemic treatment
- Any Grade  $\geq$  2 drug-related pneumonitis or interstitial lung disease that does not resolve to dose delay and systemic steroids (also see Pulmonary Adverse Event Management Algorithm)
- Any Grade 3 drug-related uveitis, pneumonitis, bronchospasm, diarrhea, colitis, neurologic toxicity (other than intracranial/brain edema), hypersensitivity reaction, or infusion reaction, regardless of duration
- Any Grade 3 non-skin, drug-related adverse event lasting  $> 7$  days, with the following exceptions:
  - Grade 3 drug-related endocrinopathies adequately controlled with only physiologic hormone replacement do not require discontinuation.
  - Grade 3 symptoms attributable to brain/intracranial edema that downgrades to Grade  $\leq 2$  within 7 days, or to Grade  $\leq 1$  or baseline within 14 days do not require discontinuation (for **rules for managing brain/intracranial edema**, see Section 6.2.5)
- Grade 3 drug-related laboratory abnormalities do not require treatment discontinuation except:
  - Grade 3 drug-related thrombocytopenia  $> 7$  days or associated with bleeding requires discontinuation.
  - Any drug-related liver function test (LFT) abnormality that meets the following criteria require discontinuation (also see Hepatic Adverse Event Management Algorithm):
    - AST or ALT  $> 5 \times$  ULN for  $> 4$  weeks
    - Any AST or ALT measurements  $> 20 \times$  ULN
    - Any Total bilirubin  $> 3 \times$  ULN
    - Concurrent AST or ALT ( $> 3 \times$  ULN) and total bilirubin ( $> 1.5 \times$  ULN)
- Any Grade 4 drug-related adverse event or laboratory abnormality, except for the following events, which do not require discontinuation:
  - Grade 4 neutropenia  $\leq 7$  days

CONFIDENTIAL

This material is the property of the NYU School of Medicine. Do not disclose or use except as authorized in writing by the study sponsor

- Grade 4 lymphopenia or leukopenia

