#### 6.2.4.2 Ipilimumab Dose Discontinuation

Ipilimumab should be permanently discontinued if any of the following criteria are met:

- Any Grade  $\geq$  2 drug-related uveitis or eye pain or blurred vision that does not respond to topical therapy and does not improve to Grade 1 severity within 2 weeks OR requires systemic treatment;
- Any Grade  $\geq$  3 bronchospasm or other hypersensitivity reaction
- Any other Grade 3 non-skin, drug-related adverse event with the following exceptions:
  - Grade 3 nausea and vomiting
  - Grade 3 neutropenia and thrombocytopenia
  - Symptomatic endocrinopathies which resolved (with or without hormone substitution)
  - Grade  $\leq$  3 symptoms attributable to brain/intracranial edema that downgrades to Grade  $\leq$  2 within 7 days, or to Grade  $\leq$  1 or baseline within 14 days after onset (for **rules for managing brain/intracranial edema**, see Section 6.2.5)
- Any drug-related liver function test (LFT) abnormality that meets the following criteria require discontinuation:
  - AST or ALT  $>$  5 x ULN for > 2 weeks

CONFIDENTIAL

This material is the property of the NYU School of Medicine. Do not disclose or use except as authorized in writing by the study sponsor

- Any AST or ALT measurements  $> 20 \times \text{ULN}$
  - Any Total bilirubin  $> 3 \times \text{ULN}$
  - Concurrent AST or ALT ( $> 3 \times \text{ULN}$ ) and total bilirubin ( $> 1.5 \times \text{ULN}$ )
- Any Grade 4 drug-related adverse event or laboratory abnormality, except for the following events, which do not require discontinuation:
  - Grade 4 neutropenia  $\leq 7$  days
  - Grade 4 lymphopenia or leukopenia
  - Isolated Grade 4 amylase or lipase abnormalities which are not associated with symptoms or clinical manifestations of pancreatitis. The Sponsor should be consulted for Grade 4 amylase or lipase abnormalities
  - Isolated Grade 4 electrolyte imbalances/abnormalities that are not associated with clinical sequelae and are corrected with supplementation/appropriate management within 72 hours of their onset
  - Grade 4 drug-related endocrinopathy adverse events such as adrenal insufficiency, ACTH deficiency, hyper- or hypothyroidism, or glucose intolerance, which resolve or are adequately controlled with physiologic hormone replacement (corticosteroids, thyroid hormones) or glucose controlling agents, respectively, may not require discontinuation after discussion with and approval from the Sponsor.

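### The recovery limits for Grade 3 brain-edema symptoms contradict each other, so the same event is or is not a DLT, and does or does not end treatment, depending on the section applied

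*Combined protocol and SAP*

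**What the plan says.** **Looser limit.** Four places accept a fall to Grade 2 or lower within 7 days, or to Grade 1 or lower or baseline within 14 days.

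- Section 6.1.1.1 (DLT definition): an edema symptom reaching Grade 2 or lower in 7 days, or Grade 1 or lower or "baseline within 14 days after onset will not be classified as DLT".
- Section 6.2.4.1 (nivolumab discontinuation): Grade 3 edema symptoms meeting the same limits, ending with "baseline within 14 days do not require discontinuation".
- Section 6.2.4.2 (ipilimumab discontinuation): an exception with the same limits for "symptoms attributable to brain/intracranial edema that downgrades to Grade" 2 or lower.
- Section 6.2.3.2 (ipilimumab restart): the same two limits.

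**Stricter limit.** The sections written specifically for edema allow less.

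- Section 6.2.5.1 withholds DLT status and permanent discontinuation on condition that "The grade 3 AE downgrades to Grade ≤1 within 7 days after onset of the event".
- Section 6.2.6 says that if symptoms have not reached Grade 1 or lower or pre-treatment baseline by day 7, "the AE will be considered a DLT (if in the Safety Lead-in cohort) and the subject will discontinue study therapy".
- Table 2, Grade 3 row, allows restart only on recovery to Grade 1 or lower or baseline within 7 days, and otherwise requires discontinuation.

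**A further DLT bullet.** Directly after the edema bullet, Section 6.1.1.1 makes a DLT of any neurological AE at or above Grade 2 that lasts more than 7 days ("grade 2 neurological AE lasting").

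**Holding at lower grades.** Section 6.2.6 opens by saying that for suspected treatment-related "symptomatic intracranial or brain edema at any time during the study, nivolumab and ipilimumab dosing should be immediately interrupted". Table 2 says no hold at Grade 1, and at Grade 2: "Consider withholding for persistent symptoms".

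**The concern.** Section 6.2.5 describes edema as common after brain radiotherapy, so these rules are likely to be used. An investigator managing a Grade 3 edema symptom has to decide whether each drug may restart or must stop for good. In the Safety Lead-In, the sponsor and the DSMC also have to decide whether the event is a DLT. If the sections disagree, a patient may lose both study drugs or keep them according to which page was consulted. The DLT count that decides whether the trial proceeds also loses a fixed definition.

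**Working it through.** The documents state no figure to reproduce here. The check sets the rules side by side and runs one patient through them.

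**Worked case.** The subject's baseline is Grade 0 or 1. A treatment-related edema symptom reaches Grade 3, falls to Grade 2 on day 6 and to Grade 1 on day 12, with no surgery, no mannitol and no prolonged high-dose steroid.

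| Decision | Looser text | Outcome | Stricter text | Outcome |
|---|---|---|---|---|
| DLT status | 6.1.1.1, edema bullet | Not a DLT | 6.2.6 expressly; 6.2.5.1 by implication | DLT |
| Nivolumab discontinuation | 6.2.4.1 | Not required | 6.2.6 and Table 2; 6.2.5.1 by implication | Required |
| Ipilimumab discontinuation | 6.2.4.2 | Not required | 6.2.6 and Table 2; 6.2.5.1 by implication | Required |
| Ipilimumab restart | 6.2.3.2 | Allowed | Table 2 | Not allowed |
| Nivolumab restart | None | – | 6.2.3.1 and Table 2 | Not allowed |

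The first four rows are conflicts on the same decision. The last row is not: Section 6.2.3.1 (nivolumab restart) already uses Grade 1 or lower within 7 days, and none of the looser texts governs nivolumab restart.

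**Conflict inside Section 6.1.1.1.** If the symptom is neurological, for example a focal deficit, it has been at Grade 2 or higher for more than 7 days. The edema bullet then says it is not a DLT and the next bullet says it is. If the symptom is nausea, which Section 6.2.5 names as an edema symptom, the neurological bullet may not apply, and the conflict is with 6.2.5.1 and 6.2.6.

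**Effect on the lead-in decision.** Section 6.1.1 continues the study at 1 or fewer DLTs in 6 and goes to redesign or stopping at 2 or more. For one disputed event, the total is the number of other DLTs plus 0 (looser) or plus 1 (stricter):

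- No other DLT: 0 or 1. Continue either way.
- One other DLT: 1 or 2. Continue under the looser limit; redesign or stop under the stricter one.
- Two or more others: redesign or stop either way.

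A single disputed event therefore decides the outcome only when there is exactly one other DLT.

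**Cross-references.** The looser bullets send the reader to Section 6.2.5 for managing edema, and that section holds the stricter rule. Sections 6.2.1 and 6.2.3 and the management-algorithm appendix (15.5) cite Section 6.1.3.7, and 15.5 also cites 6.1.3.8. Section 6.1.3 describes the Surgical Study Cohort and has no such subsections.

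**The case against.** The strongest reply is that the intended rule can be worked out. Section 6.2.5 says edema is not a DLT and does not require permanent discontinuation unless the criteria set out below it are met, and the looser bullets point to that section. This stands as evidence that the stricter limit was meant, and it supports the fix. It is not a statement of precedence, and the contrary text remains.

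A second reply is that obeying the stricter limit breaches little. For discontinuation and ipilimumab restart this is partly right: text that does not require stopping, or that permits restarting, does not forbid the opposite. But an investigator who relies on 6.2.4.1, 6.2.4.2 or 6.2.3.2 then departs from 6.2.6 and Table 2. For DLT status the reply fails, since one text says the event will not be classified as a DLT and the other says it will.

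Third, Section 6.1.1.1 leaves the final DLT decision to the sponsor and the DSMC. That limits any mechanical effect on the count, but adjudicators still need one definition.

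Three stronger readings are tempting and not supported:

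- **A stated rise in the chance of failing the lead-in.** The documents give no rate for other DLTs or for Grade 3 edema with this recovery course. Edema called common in 6.2.5 includes purely radiographic findings, and Section 6.2.7 calls symptomatic edema during radiotherapy unlikely. If the neurological bullet governs, the DLT dispute narrows to non-neurological symptoms. Any percentage would be built on assumed inputs.
- **The Grade 2 hold as an equal contradiction.** The ungraded sentence in 6.2.6 can reasonably be read as refined by Table 2, and Section 6.2.3 exempts edema from the general Grade 2 delay rule. This is a clarification.
- **Nivolumab restart (6.2.3.1) against ipilimumab restart (6.2.3.2) as a contradiction.** They concern different drugs, and a different restart limit for each is not in itself inconsistent.

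**Conclusion.** The contradiction is real for Grade 3 edema symptoms. It affects four decisions: DLT status, discontinuation of each drug, and ipilimumab restart. A symptom at Grade 2 on day 7, in a subject whose baseline is lower, gets opposite answers from the two sets of rules. Section 6.1.1.1 also contradicts itself for neurological symptoms.

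Its size is one disputed event in a rule that turns on 2 of 6, decisive for the lead-in when exactly one other DLT has occurred and subject to adjudication. No probability is attached. If the lead-in is already complete, the DLT part matters only for how its events were classified; the discontinuation and restart rules still apply to all subjects. A reader might also infer an effect on the 1-year OS analysis, but nothing in the documents shows one and none is claimed.

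**What to change.** 1. In Sections 6.1.1.1, 6.2.3.2, 6.2.4.1 and 6.2.4.2, replace the 7-day/14-day wording for Grade 3 edema symptoms with one limit: *Grade 1 or lower or baseline within 7 days of onset*. The sponsor's clinicians should confirm that this is the intended limit. It also brings the edema bullet of 6.1.1.1 into line with the neurological bullet after it.
2. Add *or baseline* to Section 6.2.3.1 and to the Grade 3 limb of 6.2.5.1, so that both match 6.2.6 and Table 2.
3. Correct the references to 6.1.3.7 (Sections 6.2.1, 6.2.3 and 15.5) to 6.2.5, and the reference to 6.1.3.8 (Section 15.5) to 6.2.6.
4. As a secondary clarification, change the opening instruction of 6.2.6 so that dosing is *interrupted according to grade as specified in Table 2*.

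The cost is wording in a protocol amendment, with no change to sample size, endpoints or analysis. Section 11 sends amendments to the IRB and Section 4.4.2 provides for re-consent after an amendment, so the edits could be combined with other planned changes.
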